Potential participants may contact the study by phone, email or through an on-line prescreen. Potential participants who learn about the study through the study website and complete a pre-screen are asked if they prefer to be contacted by phone, email or text. Study staff contact potential participants using their preference, following an approved script. Potential participants who email the study receive an email reply asking them to call the study phone number and leave a message if the call is not answered. Study staff return calls from potential participants who leave a message and if the potential participant is not reached leave a brief message reminding them about the study and request that they call back. Study staff will reach CP potential participants by phone so that they can answer CR and CP eligibility screening questions with a staff member to determine eligibility based on the inclusion and exclusion criteria.

We will use Trialfacts to promote, screen and refer eligible participants for the IDEA project. Trialfacts provides patient recruitment services for clinical trials. Ads may run on a combination of platforms including but not limited to: Facebook, Google, Google Display Network, Yahoo, Bing, Instagram, Youtube, Reddit, and Quorra. The ads will be linked to the Trialfacts landing page, which in turn is linked to the online questionnaire. Potential participants who complete the on-line screening will schedule a telephone interview with Aging with Pride: IDEA study staff to confirm their eligibility.

- b. Recruitment Materials: Study announcements will be distributed by mail and email using aging and health service agencies' contact lists and will be posted at various health, human service and community-based organizations, and published in community-based newspapers, newsletters, and social media. A short 2-minute video will be on the study webpage and a link will be put in our social media announcements. Upon expressing interest in participating, initial screening of eligibility of CPs and CRs will be conducted by telephone using a script including the purpose and design of the study, a brief review of key elements of the consent form, and an eligibility screen assessment form.
4. Study Procedures:

- a. A total of 150 CR/CR dyads will be recruited from all 50 U.S. states and territories and randomly assigned to one of two treatment arms: IDEA (75) or RDAD (75).

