  - i. RDAD: For the **RDAD group** we will use the detailed treatment manual developed and used for earlier translational research (IRB 41906-D, From Evidence-Base to Practice: Implementing RDAD in AAA Community-Based Services, PI: [name]). The manual includes text for the coaches, graphic illustrations of exercises, handouts, and process/treatment fidelity forms. CPs are taught how to encourage and help individuals with dementia with their exercises, and behavioral plans are developed and implemented. The exercise component of RDAD includes aerobic/endurance activities, strength training, and exercises to improve balance and flexibility. Exercises are introduced incrementally and individualized to meet the needs of each person. Each exercise is first demonstrated by the coach, then practiced by the CR and CP. Coaches monitor the exercises closely in order to ensure that they are practiced safely and correctly. In the proposed study, both CRs and CPs will practice and demonstrate the exercises at each session, and both will be encouraged to engage in a minimum of 30 minutes of moderate-intensity exercise every day. In the behavior management component of RDAD, the ABC technique is applied. CPs are taught to identify the antecedent (A) to a CR behavioral issue or problem (B) as well as the consequences (C) of the behavior. CPs are instructed to identify and modify CR behavioral problems that can impair day-to-day function, adversely affect CP-CR interactions, and interfere with exercise participation. They are given specific training in how to identify precipitants of CR problem behaviors, and how to modulate their own responses to these problems. CPs are also encouraged to identify pleasant activities that can be incorporated into the exercise program for both persons in the dyad. Finally, CP issues, such

as depression, burden, and stress, are assessed and sources of support are identified.

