- ii. IDEA: For the **IDEA group** we will use the existing detailed treatment manual, incorporating three specific risk factors that have been empirically derived and are LGBT-specific, into the behavioral component of the intervention. These include: 1) identity management; 2) stigma-related adverse or traumatic life events; and 3) lack of social support. The three LGBT-specific components are integrated into the existing training and exercises so that the time and exposure to intervention training are equivalent across RDAD and IDEA. As part of the behavior management component using ABC technique, CPs are taught how to assess and respond to CR's LGBT identity management challenges and the impact of adverse or traumatic life events, as well as how to build and sustain social support to support exercise adherence for CRs and CPs. To further increase exercise adherence and support from peers and family members, an AD/RD education DVD will be provided; the educational component includes topics such as symptoms, progression, and treatment of dementia; the effect of exercise and support on AD/RD. IDEA coaches will be trained to use motivational interviewing techniques focused on person-centered engagement, development of participant self-efficacy, and support mobilization to address barriers and facilitators to positive change in primary outcomes. For LGBT populations these may include lack of empowerment due to historical trauma, stigma, non-disclosure of stigmatized identities, and social isolation.
- d. Covid-19 adaptation: During the COVID-19 outbreak the intervention delivery procedures described above will be conducted virtually by a video-conferencing platform. We will ask participants if they have a computer, iPad or cell phone capable of using any of these video conferencing platforms. For those participants who do not have video conferencing capability or prefer not to use video conferencing we will resume in-home sessions when it is deemed safe to do so according to the CDC.
- e. Post-treatment assessments: Research staff will conduct, via telephone, post-treatment assessment #1 after the in-person sessions, post-treatment assessment #2 after the phone sessions, and a follow-up assessment at 13th month with CP participants to evaluate treatment effectiveness on outcomes for CR and CP participants. Participants will receive \$25 for each assessment, described as reimbursement for time and expertise in research topics. Change of

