- a. Privacy Protections: Only UW research staff members will contact study subjects. All intervention sessions will be conducted by trained research staff in a place where privacy is ensured. Coaches will ensure that sessions remain confidential and that they are in a place where others cannot observe. Sessions will be audio recorded only for the purpose of monitoring treatment fidelity. Assessment data collected will be available only to the project staff and investigators directly involved with this study. No others will have access to the data. Collected data are confidential. Each subject will be assigned a unique identification number. Direct identifiers including contact information will be stored separately from the data collected through questionnaires, interviews, and assessments. The data cannot identify a subject without having access to the link between the identification number and the direct identifiers. A study subject cannot be identified by anyone except the UW lead researchers and authorized research staff members who have legitimate access to the single record identifying subjects by their research ID number. This record will be stored and maintained separate from all data and other information gathered. All data will be stored in encrypted computer files and records will be identified by a unique identification number that are assigned by the study. The data files will not contain any identifying information.
- b. All members of the research team will complete required training in human subjects and HIPAA, including training in data management and confidentiality.
- c. Retention of identifiers and data: We will not destroy any identifiers (or links between identifiers and data/specimens) and data that are part of research records until after the end of the applicable records retention requirements.

9. Risk/Benefit Assessment:

- a. Anticipated Risks: Subjects in the study may be inconvenienced or experience psychological discomfort related to assessment questions including previous experiences of LGBT-specific adverse experiences and everyday discrimination. Subjects may also experience mild physical discomfort related to engaging in new physical exercise activities. These problems have not previously occurred in Drs. [name] or [name]'s studies, and we estimate the risks to be minimal. Subjects are informed that they are free to not answer any question and not to participate in any exercises.

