exception being incidents of abuse of a dependent adult or minor child and risks of imminent harm to others or to the subject. All researchers have completed training in research with human subjects.

10. Analysis Plan: All participant data will be included in the study, according to the intent-to-treat principle, after excluding participants who withdrew prior to completing their baseline assessment. Analysis will be completed using Stata/MP 16.1 (StataCorp, 2019). To assess whether randomization of patients was successful, the two treatment groups will be compared by baseline demographics and clinical characteristics using two-sample *t*-tests, Chi-Square tests of independence, or Fisher's exact tests as appropriate. To test efficacy of the interventions, we will use linear mixed models to test the short- and long-term intervention effects on outcomes, with time treated as a categorical variable. The models included random intercepts and slopes for each participant to account for individual variability at baseline and change over time of the outcome variables and included baseline scores of the outcomes as fixed effects. Mixed-effects logistic regression models were estimated for binary outcomes, and continuous outcomes were estimated with mixed-effects linear regression models. Moderation effects were evaluated using interaction terms in the linear mixed models. The proposed sample size with a two-sided significance of 5% and a statistical power of 80% is sufficient to detect a small effect ( $d= 0.25$ ), which is greater than a minimal clinically important difference level. The statistical significance of all hypothesis tests were set at two-sided level of  $p = .05$ .

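### The efficacy model makes no allowance for dyads sharing a coach; if coaches are specific to one arm, the true type I error exceeds 5%, and the plan does not say how coaches are allocated

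*Combined protocol and SAP*

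**What the plan says.** **Model.** Section 10 (Analysis Plan) specifies linear mixed models with categorical time, baseline scores as fixed effects and "random intercepts and slopes for each participant". It names no coach term, no cluster-robust variance and no design effect in the power statement. On the error rate it says "The statistical significance of all hypothesis tests were set at two-sided level of" p = .05.

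**Delivery.** Section 8.a says "All intervention sessions will be conducted by trained research staff in a place where privacy is ensured". Section 4.c sets nine one-hour sessions over six weeks, then four phone calls; it does not name the caller. Under Section 4.c.i (RDAD), "Each exercise is first demonstrated by the coach, then practiced by the CR and CP", and the coach monitors the exercises closely. Section 4.c.ii adds that "IDEA coaches will be trained to use motivational interviewing techniques", with the aim of improving the primary outcomes; Section 4.c.i describes no such training for RDAD.

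**Not stated.** The number of coaches, dyads per coach, how dyads are assigned to coaches, whether a coach works in one arm or both, and any expected coach ICC.

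**The concern.** Coaches differ in skill, and both programmes work through what the coach does. Dyads with the same coach may therefore have correlated outcomes. A random intercept and slope per participant model the correlation among one person's repeated measures; they leave different dyads independent.

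If each coach works in only one arm, differences between coaches fall entirely into the arm contrast. Ignoring them makes the standard error too small, the intervals too narrow and false positives more frequent. The plan compares two programmes matched on time and exposure and looks for a small effect (d = 0.25), and a small contrast is where an understated standard error misleads most. The same model serves the primary and secondary outcomes, though the coach ICC may differ between them and be near zero for some.

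**Working it through.** **Inputs.** From the documents: 75 dyads per arm (Section 4.a); two-sided 5%, d = 0.25, 80% power (Section 10). Assumed, because the documents give neither: K coaches per arm, from 3 to 25, and ICC of 0.02 or 0.05. The check also assumes one coach per dyad, equal caseloads and a simple two-sample comparison, so the ICC has to be read on the scale of the residual variation in the planned baseline-adjusted model.

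**The plan's own figure.** In a plain comparison, power = Φ(0.25 × √(75/2) − 1.96) = Φ(1.531 − 1.960) = 33.4%, not 80%. The stated 80% can be reached only with inputs the plan does not give, for example the mean of three follow-ups adjusted for two baselines with a within-person correlation of at least 0.57. That is a separate matter; what counts here is that the power statement includes nothing for coaches.

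**Case 1: coaches nested in arm.** With m = 75/K dyads per coach, DE = 1 + (m − 1) × ICC. The true standard error is √DE times the model's, and actual alpha = 2 × [1 − Φ(1.96/√DE)].

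| K per arm | m | DE, ICC 0.02 | Alpha | DE, ICC 0.05 | Alpha |
|---|---|---|---|---|---|
| 3 | 25 | 1.48 | 10.7% | 2.20 | 18.6% |
| 5 | 15 | 1.28 | 8.3% | 1.70 | 13.3% |
| 10 | 7.5 | 1.13 | 6.5% | 1.325 | 8.9% |
| 25 | 3 | 1.04 | 5.5% | 1.10 | 6.2% |

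Example: K = 5, ICC 0.05 gives DE = 1 + 14 × 0.05 = 1.70 and 1.96/√1.70 = 1.503, hence 13.3%. At ICC 0.01 with 5 coaches per arm alpha is 6.6%; at ICC 0 it is 5.0%. Effective size per arm at ICC 0.05 is 75/DE: about 34, 44 and 57 for K = 3, 5 and 10. Plain-comparison power for K = 5, ICC 0.05 falls from 33.4% to 21.6%.

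**Case 2: the same coaches in both arms, balanced, one common effect.** The coach effect cancels from the contrast, but the unadjusted model still counts it as noise. Actual alpha = 2 × [1 − Φ(1.96/√(1 − ICC))], which is 4.8% at ICC 0.02 and 4.4% at ICC 0.05.

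**Case 3: shared coaches who do better with one programme than the other.** Take total coach variance 0.05, of which 0.02 is coach-by-arm, and 5 shared coaches. The ratio of true to model variance is (1 − 0.05) + 15 × 0.02 = 1.25, and 2 × [1 − Φ(1.96/√1.25)] = 8.0%. With 3 shared coaches the ratio is 0.95 + 25 × 0.02 = 1.45 and alpha is 10.4%.

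**Simulation.** A t-test on one follow-up, 8,000 replicates per setting, agrees: with K = 5 and ICC 0.05, 13.4% nested and 4.5% crossed. In a separate run of 6,000 replicates per setting, a test at the coach level held 4.9% to 5.1% in the nested settings with 3, 5 and 10 coaches per arm at ICC 0.05.

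**Price of a valid analysis.** In the nested case with 2(K − 1) degrees of freedom, intervals widen by √DE × t(0.975)/1.96. At ICC 0.05: K = 3, 1.483 × 2.776/1.96 = 2.1; K = 5, 1.304 × 2.306/1.96 = 1.5; K = 10, 1.151 × 2.101/1.96 = 1.2.

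**The case against.** The documents do not establish that coaches are arm-specific. The mention of IDEA coaches may mean a separate group, or simply coaches while they deliver IDEA. Section 9.b describes training for coaches without dividing them by arm, and Section 7 has the coach take consent with no reference to arm. If the same coaches serve both arms in balance, the planned test errs on the safe side.

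The number of coaches may also be large. Recruitment covers all states and territories with delivery at home, which could mean many coaches with few dyads each, although video delivery during the pandemic could reduce the number. The larger figures need 3 to 5 coaches per arm and ICC 0.05. Manuals, fidelity forms and audio monitoring may keep the ICC low. Finally, the formula is for a simple comparison, not the planned longitudinal model.

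All of this stands, and it makes the size conditional. It does not close the gap. Crossing protects the error rate only if it is balanced and there is no coach-by-arm variation, and the plan states neither. Fidelity procedures reduce coach variance but do not show that it is zero.

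**Conclusion.** The planned model omits a plausible source of correlation, and the plan does not give the facts needed to judge its effect. With coaches nested in arm, actual alpha runs from 5.5% to 18.6% over 3 to 25 coaches per arm and ICC 0.02 to 0.05. With balanced shared coaches and a common effect it is 4.4% to 4.8%. With shared coaches and some coach-by-arm variation it can again exceed 5%.

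A reader might infer that the standard errors are too small and that the 5% level fails. The documents do not support this as a fact: it needs arm-specific coaches or coach-by-arm variation, several dyads per coach, and an ICC above zero, none of which they state. In the balanced shared case the direction is the opposite. A reader might also infer that coaches make the four maintenance calls; the caller is not named.

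The point is worth acting on because the remedy lies in the analysis alone and is valid under either allocation.

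**What to change.** - State how many coaches there are, how dyads are assigned to them, and whether a coach delivers one programme or both. Record the coach for each dyad; the documents do not say whether this is already done.
- Add a coach random intercept to the mixed models: coach within arm if each coach delivers one programme; coach plus coach-by-arm if coaches deliver both.
- Use Kenward-Roger or Satterthwaite degrees of freedom for the linear models.
- Make the power statement reflect the same structure, with the assumed number of coaches and ICC given.

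The work is SAP wording and one variable in the data set. The statistical cost depends on the number of coaches. In the nested case at ICC 0.05, intervals are about 1.2 times as wide with 10 coaches per arm, 1.5 times with 5 and 2.1 times with 3. With few coaches that is a substantial loss of precision, and it should be faced in the power statement before the analysis.

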  - a. Aim 1. Test the translation of RDAD and IDEA programs designed to increase physical activities of older adult care receivers (CRs) with AD/RD and their CPs. Aim 2. Evaluate the short- and long-term effect of RDAD and IDEA on primary (*physical activity for CRs*) and secondary outcomes (*memory-related behavioral disturbances, physical functioning, and QOL for CRs; depressive symptomatology; perceived stress for CRs*). Aim 3. Test the moderating roles of CR-CP characteristics and severity of CR AD/RD on the treatment effect of RDAD and IDEA.
  - b. Study design: This study will utilize a 2-group randomized, single blind with staggered multiple baseline design and three follow-up assessments.

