## 2. Participants

- a. General characteristics: 150 dyads of CRs with AD/RD aged 50 or older and their CPs (N=300) will participate in the study. Either the CR or CP will be sexual/gender minority.
- b. Inclusion Criteria: Inclusion criteria for CR and CP: Either CR or CP is a sexual or gender minority. Inclusion criteria for CR: 1) age at enrollment is 50 years of age or older; 2) living in the community (not in a long-term care facility with nursing home level care); 3) have Alzheimer's disease or other dementia. Based on the definition of dementia suggested by Alzheimer's Association and scientific literature, dementia will be determined 1) by asking CP the current diagnostic

status of CR's AD/RD or 2) by asking CP whether CR has any difficulties in the domains of dementia/memory loss AND needs any help in daily activities. This method has two key aspects: (1) it precludes considerable increased costs that would be necessitated by providing a physical exam and (2) avoids unnecessary delays (and potentially loss of subjects) by scheduling an exam or waiting for receipt of patient charts. Inclusion criteria for CP: 1) willing to spend at least 30 minutes per day for study activities or willing to coordinate with CR's networks to do so; 2) providing care to the CR; 3) living in the community, not in a nursing home or long-term care facility.

- c. Exclusion Criteria: Exclusion criteria for CR and CP: 1) having plans to move to a long-term care setting within 6 months of enrollment; 2) having a known terminal illness (with death anticipated within the next 12 months); 3) having been hospitalized for a psychiatric disorder in the 12 months prior to baseline; 4) actively being suicidal and having major hallucinations or delusions (occasional hallucinations or delusions are common symptoms of dementia. CR will be eligible if CR's hallucinations or delusions do not prevent participation in a low impact exercise); and 5) having any physical limitations/chronic conditions preventing participation in a low impact exercise program.
- d. Number of Subjects: 150 dyads (N=300)
  - i. IDEA Intervention Arm: 75 CR/CP dyads
  - ii. RDAD Intervention Arm: 75 CR/CP dyads

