- b. Pre-Treatment (baseline) assessment: Pre-treatment (baseline) assessments #1 and #2: Upon the random assignment, a research coordinator will contact subjects and schedule two pre-treatment assessments with a 6-week interval via telephone. CP will complete a 40 to 60-minute questionnaire via telephone for each assessment.
- c. Interventions: RDAD and IDEA are 9 1-hour sessions, conducted over 6 weeks in the participants' homes or a place of their choice where privacy is ensured. The sessions will be conducted twice a week for the first three weeks; once a week for the next three weeks; in the 12-week maintenance phase 4 15- minute follow-up phone calls will occur once a month for the next 4 months.

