address pre-stamped and addressed postcards will be given to all participants to be used to notify project staff for change of address and contact information.

5. Outcome Measures:

- a. Change in physical activity (CR) [Time Frame: Baseline (pre-treatment) to 13, 30, and 52 weeks post-treatment]
  - i. Measured by the number of days of exercise for at least 30 minutes in the past week. Higher scores indicate more days of activity.
- b. Change in physical functioning (CR) [Time Frame: Baseline (pre-treatment) to 13, 30, and 52 weeks post-treatment]
  - i. Assessed using mean score on physical functioning subscale of SF-36 (Medical Outcomes Study [MOS] 36-Item Short Form), consisting of 10 items assessing if participants' health limit them in activities such as walking, climbing, lifting, etc. on a 3-point scale ranging from 'yes, limited a lot' to 'no, not limited at all.' Higher scores indicate higher physical functioning.
- c. QOL (CR) [Time Frame: Baseline (pre-treatment) to 13, 30, and 52 weeks post-treatment]
  - i. Quality of life was evaluated using summed scores on the Quality of Life in Alzheimer's Disease (QOL-AD), a 13-item measure widely for quality of life in interventions with persons with AD/RD. Range of scores 13-52 with higher scores indicating better quality of life.
- d. Memory-related behavioral disturbances (CR) [Time Frame: Baseline (pre-treatment) to 13, 30, and 52 weeks post-treatment]
  - i. Assessed using mean scores on the memory-related subscale (7 items) of the 24-item Revised Memory and Behavior Problem Checklist (RMBPC). Higher scores indicate higher memory-related behavioral disturbances.
- a. Depressive symptomology (CP) [Time Frame: Baseline (pre-treatment) to 13, 30, and 52 weeks post-treatment]
  - ii. Depressive symptomology was assessed by summed score on the 10-item Center for Epidemiological Studies-Depression Scale (CESD-10), validated among older adults and commonly used with caregiver populations. Range of scores 0-27 with higher scores indicating higher levels of depression.
- b. Perceived stress (CP) [Time Frame: Baseline (pre-treatment) to 13, 30, and 52 weeks post-treatment]
  - iii. Assessed with mean scores on the Perceived Stress Scale (PSS) is a 14-item self-report measure designed to measure nonspecific, appraised stress during the past month. Higher scores indicate more stress.

6. Identifiability of data:

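### The 80% power claimed for d = 0.25 does not follow from 75 dyads per arm, because the powered contrast and its assumptions are not stated

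*Combined protocol and SAP*

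**What the plan says.** Section 10 (Analysis Plan) contains the only sample-size justification: "The proposed sample size with a two-sided significance of 5% and a statistical power of 80% is sufficient to detect a small effect", given as d = 0.25. It adds that this exceeds a minimal clinically important difference, but gives no value for that difference.

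The design elements that bear on the figure are elsewhere:

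- Section 2.d: "IDEA Intervention Arm: 75 CR/CP dyads", and the same number for RDAD.
- Section 1, study design: "This study will utilize a 2-group randomized, single blind with staggered multiple baseline design and three follow-up assessments".
- Section 1, Aim 2: "Evaluate the short- and long-term effect of RDAD and IDEA on primary" and secondary outcomes.
- Section 4.b: "Upon the random assignment, a research coordinator will contact subjects and schedule two pre-treatment assessments with a 6-week interval via telephone".
- Section 4.c.ii: the LGBT-specific content is built into the existing sessions "so that the time and exposure to intervention training are equivalent across RDAD and IDEA".
- Section 5.a, the primary outcome: "Change in physical activity (CR) [Time Frame: Baseline (pre-treatment) to 13, 30, and 52 weeks post-treatment", and "Measured by the number of days of exercise for at least 30 minutes in the past week".

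The analysis in section 10 is a mixed model with categorical time, random intercepts and slopes, and baseline scores as fixed effects. Dyads who withdraw before completing baseline are excluded.

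**The concern.** In a two-arm randomised trial, a power statement will be taken to refer to the comparison of the arms. A standardised difference of 0.25 with 75 per arm is well short of 80% power in a simple comparison, so the figure must rest on something more: baseline adjustment, averaging over visits, a within-dyad comparison, or a different effect-size scale. Section 10 does not say which.

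This matters here because both arms are active and matched for time and exposure. A small difference is plausible, and a non-significant result is easily over-read. A reader who believes the trial had 80% power for 0.25 SD will take a null result as fairly good evidence against a difference of that size. The precision of the trial depends heavily on the contrast, so the reader needs to know which one was planned.

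**Working it through.** **Inputs from the documents.** Two-sided 5%, d = 0.25, 75 dyads per arm, two baselines, three follow-ups (13, 30 and 52 weeks), baseline adjustment.

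**Assumed, because the plan gives no value.** Correlation r = 0.5 to 0.7 between any two assessments (compound symmetry), no loss, and d in SDs of a single assessment.

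**1. Stated inputs only.** The standard error is √(2/75) = 0.163 SD, so the noncentrality is 0.25/0.163 = 1.53. With the noncentral t on 148 df, power is 33%. The detectable d at 80% power is 0.46, and d = 0.25 needs 253 dyads per arm. The stated 80% is not reproduced. Counting all 300 individuals (150 per arm) gives only 58%.

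**2. Crediting baseline adjustment and repeated visits.** For the mean of m follow-ups adjusted for k baselines, the variance relative to a single assessment is

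v = [1 + (m − 1)r]/m − k r²/[1 + (k − 1)r]

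and the noncentrality is 0.25/√(2v/75). Two examples:

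- One visit, one baseline, r = 0.5: v = 1 − 0.25 = 0.75, standard error √(0.75 × 2/75) = 0.141, noncentrality 1.77, power 42%.
- Three-visit average, both baselines, r = 0.6: v = 2.2/3 − 2(0.36)/1.6 = 0.283, standard error 0.087, noncentrality 2.88, power 82%.

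| Contrast (75 per arm) | Power at r = 0.5 / 0.6 / 0.7 | Detectable d | Dyads per arm for 80% | r that gives 80% |
|---|---|---|---|---|
| One visit, one baseline | 42 / 48 / 57% | 0.40 / 0.37 / 0.33 | 190 / 162 / 130 | 0.84 |
| One visit, both baselines | 46 / 54 / 65% | 0.38 / 0.34 / 0.30 | 169 / 140 / 108 | 0.80 |
| Three-visit average, one baseline | 65 / 70 / 78% | 0.30 / 0.28 / 0.26 | 106 / 95 / 79 | 0.72 |
| Three-visit average, both baselines | 75 / 82 / 90% | 0.27 / 0.25 / 0.22 | 85 / 73 / 58 | 0.58 |

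A simulation of the adjusted analysis (8,000 runs per cell) agrees to within about two percentage points. A joint 3-df test of the three visits, with a constant difference of 0.25, has 48-61% power (one baseline) or 58-77% (both).

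**3. Loss.** Baselines follow randomisation and pre-baseline withdrawals are excluded, so the analysed number can fall below 75. At an assumed 20% loss (60 per arm) and r = 0.5 to 0.7, one-visit power is 35-48% or 38-55% (one or both baselines), and power for the average is 56-68% or 65-82%.

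**4. Random slopes.** The planned model includes them, and they weaken the correlation with late visits. Assume an intercept share of 0.5 to 0.7 and a slope variance of 0.1 to 0.2 of the baseline variance per year². With both baselines, power is then 38-56% at week 52 and 67-85% for the average.

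**5. Other readings that reach 80%.**

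- A pooled pre-post test on all 150 dyads, with d in SDs of change: 86% (128 dyads suffice for 80%).
- 0.25 meant as Cohen's f, which is d = 0.5: 86% with 75 per arm (64 per arm suffice for 80%).
- A group-by-time F test at f = 0.125, with three or more measurements and a correlation of at least 0.3: 81% or more.

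Each is a different claim from the one written.

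**6. Precision.** The 95% half-width is 1.976 × √(2v/75). It is 0.21 to 0.28 SD for one visit and 0.15 to 0.21 SD for the three-visit average. If the SD of exercise days were 2 to 3 (an assumption), d = 0.25 is 0.5 to 0.75 day per week, while the one-visit detectable 0.30 to 0.40 SD is 0.6 to 1.2 days.

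**The case against.** The strongest reply is that this is missing detail, not a wrong number. The plan has a mixed model over three follow-ups and refers to baseline scores in the plural. The contrast that uses most of those data, the three-visit average with both baselines, has 75-90% power over the assumed range and so brackets 80%. The range 0.5 to 0.7 is itself unsourced: at r = 0.8 with both baselines, even one visit reaches 81%. Aim 2 and the multiple-baseline design can also be read as within-dyad questions. Within one arm of 75, the mean of three follow-ups against the mean of two baselines would have 91-99% power on the same assumptions (d in single-assessment SDs). And rewording the sentence changes no estimate or interval.

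Much of this stands. The figure is not impossible, the correlation is an assumption, and the one-visit test is not the only reading. But section 10 treats time as categorical and asks about short-term and long-term effects, which makes a by-visit comparison of the arms a fair reading. It never names a visit average. On the by-visit reading the claim fails unless r is about 0.80 or more. If a within-dyad test was meant, the plan states no power at all for IDEA versus RDAD, the only comparison that randomisation protects.

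**Conclusion.** The concern holds. The 80% figure does not follow from what the plan states, and on the by-visit reading of the between-arm test it is too high across the assumed range of correlation. A true one-visit difference of 0.25 SD would be missed 35-58% of the time, not 20%. For the three-visit average the miss rate is 22-35% with one baseline and 10-25% with both, so the stated power is attainable there, at r of at least about 0.72 or 0.58.

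These figures rest on assumed compound symmetry, r of 0.5 to 0.7 and no loss. Loss lowers all of them. The 33% for the unadjusted comparison is a reference value, not the verdict, since the plan does adjust for baseline. Because 0.25 is said to exceed the minimal important difference, power at that smaller difference is below whatever power applies at 0.25.

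**What to change.** Replace the sentence in section 10 with a detectable difference for a named between-arm contrast. Suggested wording: *With 75 dyads per arm (two-sided 5%, 80% power), the detectable IDEA-RDAD difference for [contrast and visits] is d = [value], in SDs of [quantity], assuming a correlation of [value and source], [one/both] baselines and [x]% loss.*

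Reference values for one visit, at an assumed r of 0.7 down to 0.5, are 0.33-0.40 with one baseline, 0.30-0.38 with both, and 0.46 unadjusted. With an assumed 20% loss they are 0.37-0.45, 0.34-0.42 and 0.52.

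The correlation could come from earlier RDAD data. The two baselines pooled over arms could also be used, but a 6-week correlation is likely to exceed the one with week 52.

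Keep d = 0.25 only if the named contrast and its supported assumptions deliver 80%. Examples are the three-visit average with both baselines at r of at least about 0.58 (0.68 with 20% loss), or one visit with no loss at about 0.80 with both baselines or 0.84 with one. If the figure came from a pre-post test or from Cohen's f, say so and report between-arm power separately. Give the minimal important difference as a value.

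The cost is one paragraph, with no extra dyads and no change to the model. The stated figure will be less favourable unless the assumptions support 0.25.
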